10.2 Secondary Efficacy Endpoint and Analysis

Secondary efficacy analyses will be conducted for the safety populations, unless otherwise stated.

The secondary endpoints in this study are:

- Proportion of patients eligible for sequence analysis with SARS CoV-2 VOC/VUI on the earliest possible sample.

The proportion of patients with VOC/VUI will be summarized showing the counts and percentages of patients by each variants based on WHO classification and Pango sub-lineage for the earliest possible VOC/VUI sample including baseline. A data listing including WHO label and Pango sub-lineage will be provided.

- Proportion of patients with undetectable virus (i.e. viral load < LLOD)

Summary of proportion of patients with undetectable virus would be based on safety population and summarized by Day 7, 14 and 28 (+/-2 days).

- Clinical outcomes through Day 28 post-sotrovimab treatment:

The following clinical outcomes will be summarized by count and percentage of patients and its 95% CI by VOC/VUI, Non-VOC/VUI, and Overall:

- Proportion of patient with all-cause hospital admissions
- Proportion of patient with COVID-19 related hospital admissions.
- Proportion of patients requiring new or increased oxygen support (supplemental oxygen [not high flow], non-invasive ventilation or high-flow, invasive mechanical ventilation, or Extracorporeal membrane oxygenation [ECMO])
- Proportion of patient with all-cause ICU admissions.
- Proportion of patient with COVID-19 related ICU admissions.
- Proportion of patient who died through Day 28.
- Proportion of patient who died through Day 28 due to COVID-19.

In addition, the clinical outcomes would also be summarized by VOC/VUI variants and also by Medical Condition/Comorbidity.

The above outputs for Clinical outcomes will be based on the Safety Completers Population for the Interim Analysis and safety population for Final Analysis.

Data listings on clinical outcomes separately for hospital admission, ICU admission, oxygen support, death will be listed.

This document is confidential.

- AA (detected at >5% allelic frequency) changes in the SARS-CoV-2 spike protein in samples collected at Day 7, 14 and 28 (+/-2 days) compared to baseline following sotrovimab administration for samples with viral loads above the threshold of the sequencing assay
- AA changes in the SARS-CoV-2 spike consensus sequences from baseline in samples where viral load is insufficient for >5% allelic frequency analysis but sufficient to generate consensus level sequencing data

For the above endpoints, Baseline and post-baseline (Day 7, 14 and 28 (+/-2 days)) AA substitutions will be summarized by showing the counts and percentages of patients in spike and epitope substitutions separately for Minority species (>5% allelic frequency) as well as consensus sequence (>50% allelic frequency).

Treatment emergent AA substitutions in spike as well as epitope for minority species and consensus sequence would be listed separately.

A similar baseline and post-baseline AA substitutions summary were presented by VOC/VUI variants for the interim but will not be included in the final analysis..

Data listings will be provided for all the baseline and post-baseline AA substitutions in spike as well as epitope for minority species and consensus sequence separately.

- Viral load

Absolute and change from baseline viral load summaries will be based on Safety and Virology population respectively on log10 copies/mL.

An overall summary of viral load (log10 copies/mL) with actual values and change from baseline values of viral load as well as by Day 0, Day 7, 14 and 28 (+/-2 days) using descriptive statistics will be displayed and presented graphically over time.

In addition, viral load (log10 copies/mL) with actual values and change from baseline values will also be summarized by VOC/VUI variants, and for Epitope Substitutions by Residue and presented graphically over time. Also, individual subject profile plots of viral load by VOC/VUI will be graphically presented based on viral load imputed values.

.A summary of viral load (log10 copies/mL) with actual values using descriptive statistics will be presented for the subset of subjects who had missing viral load at Baseline, and separately for the subset of subjects who had a viral load available at Baseline.

Listings will be provided for all viral load data as well as a separate listing including only epitope substitution.

This document is confidential.

- **Viral Rebound**

A subject has experienced a virologic rebound when following conditions are met:

If subject is in the safety population and:

- Viral load increases $>1 \log_{10}$ copies/mL at any point in time following any previous sample.
OR
- Viral load becomes quantifiable after having been below the limit of quantification (LLOQ) or limit of detection (LLOD).

A table will be summarized with number of subjects who met viral rebound and will also list out their viral load information.

11. Safety

All safety analyses will be conducted using the safety population.

In this study, only events considered related to sotrovimab are collected and referred to adverse drug reactions (ADRs). Therefore, any reference to AE in subsequent sections indicates ADR, unless otherwise stated.

Safety will be assessed on the basis of reporting and analyzing of AE .

Only descriptive statistics will be produced.

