8.2.1. Inclusion Criteria

1. Adult patients aged ≥ 18 years
2. IC (as defined in the clinical commissioning policy [NHS England, 2022])
3. A positive PCR or antigen test for SARS-CoV-2 through clinical testing or routine screening undertaken as part of clinical management
4. Prescribed treatment with sotrovimab as standard of clinical care
5. Able to provide informed consent and willing to adhere to study-related procedures

The list of IC population eligible to receive sotrovimab will be derived from the IC cohorts outlined in the interim Clinical Commissioning Policy: neutralising monoclonal antibodies or antivirals for non-hospitalised patients with COVID-19. Patient cohorts considered at highest risk from COVID-19 and to be prioritised for treatment with nMABs [NHS England, 2022]. The list may include specific IC patients within the following cohorts:

- Patients with a solid cancer
- Patients with a haematological disease and stem cell transplant recipients
- Patients with renal disease
- Patients with liver disease
- Patients with immune-mediated inflammatory disorders (IMID)
- Immune deficiencies
- HIV/AIDS
- Solid organ transplant recipients

Of note, the criteria for the IC cohorts are subject to change as they will follow the latest NHS guidance. The protocol will not be amended to accommodate updates to MHRA guidance, but the criteria will be updated accordingly in the study reference manual.

The decision to treat patients with sotrovimab will be made prior to and independently from the decision of enrolling patients into this study by the patient's healthcare team. Informed consent form and baseline sample collection will be taken prior to sotrovimab administration or if not possible, then either during sotrovimab infusion or as close as possible to the end of sotrovimab infusion (within ≤ 2 hours of the end of the sotrovimab infusion). This study will therefore include patients who have received sotrovimab dosed as part of their standard clinical care

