| 0.950 | 500 | 0.078 | 0.250 | 0.213 | 0.291 |
| 0.950 | 500 | 0.089 | 0.500 | 0.455 | 0.545 |
| 0.950 | 500 | 0.089 | 0.520 | 0.475 | 0.564 |
| 0.950 | 500 | 0.072 | 0.800 | 0.762 | 0.834 |
| 0.950 | 500 | 0.065 | 0.850 | 0.815 | 0.880 |

- Confidence level is the proportion of CIs (constructed with this same confidence level, sample size, etc.) that would contain the population proportion.
- N is the size of the sample draw from the population.
- Width is the distance from the lower limit to the upper limit.
- Actual width is the value of the width that is obtained from the procedure.
- Proportion (P) is the assumed sample proportion.
- Lower Limit is the lower limit of the CI.
- Upper Limit is the upper limit of the CI.

Using an estimate of 20% of patients being lost to follow-up, the plan will be to increase recruitment up to 625 patients to meet the target sample size of 500. It is also anticipated that in some patients, the viral load in samples collected at days 7, 14, and 28 (+/-2 days) will be too low for determination of the variable of interest. While undetectable viral load is a goal for treatment, this would further reduce the number of patients contributing to the assessment of the primary endpoint. Nonetheless, there remains adequate precision if

there are fewer patients contributing to analyses at day 7, for example (e.g. if there were 400 patients with a detectable viral load and 50% had AA changes that meet the criteria of interest, then the precision would be 95% CI 45.0-55.0%).

As a sentinel surveillance study, the aim will be to collect 500 (and up to 625) patients over the course of a year across the GB to meet the target sample size. Flexible enrolment caps per site and per month may be considered. The aim is to ensure continuous enrolment with appropriate geographical representation over the 12-month study period, to reflect the fast evolving COVID-19 pandemic. In addition, the target sample size will be re-assessed after the first 200-300 patients are enrolled in regard to progression towards achieving the primary objective, with the potential to decrease or increase the target number accordingly.

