7.2 Safety Set

The Safety Set (SS) will include all participants who were enrolled and exposed to study intervention.

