7.3 Virology Set

The Virology Set (VS) will include all participants who were enrolled and exposed to study intervention with a positive PCR test by GOSH qPCR having Viral load above lower limit of detection (i.e., viral load \geq LLOD) as threshold at baseline.

This document is confidential.

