8.2 Key Definitions

End of Study (EOS)

The EOS is defined as the date the last participant completes the last visit as shown in the Schedule of Activities in [Section 4.8](#).

Study day

Event date can be adverse events, labs, or any other assessments during the study.

If the event date \geq date of first dose of sotrovimab, study day = event date – date of first dose of sotrovimab + 1.

If the event date $<$ date of first dose of sotrovimab, study day = event date – date of first dose of sotrovimab.

Baseline Value

Baseline value will be defined as the last non-missing value recorded prior to sotrovimab administration or as close as possible to the end of sotrovimab infusion.

Retrospective collection of baseline data with the patient or directly with patient HCP will be conducted when not possible at Day 0. In all cases baseline is defined to be Day 0.

Change from Baseline (CFB)

CFB = Post-baseline value – Value at baseline

Treatment Emergent

Treatment emergent amino acid substitutions include subjects where baseline and post-baseline records exist.

Treatment emergence for consensus will include baseline records of allelic frequency $>5\%$ and post-baseline $>50\%$ as thresholds, whereas treatment emergence for minority will include baseline records of allelic frequency $>5\%$ and post-baseline $>5\%$ as thresholds.

Consensus sequence is defined as allelic frequency $>50\%$ and minority species with allelic frequency $>5\%$.

Lower Limit of Detection (LLOD)

LLOD of the assay is defined as 453 copies/mL (equivalent to Ct=38).

Lower Limit of Quantification (LLOQ)

LLOQ of the assay is defined as 1570 copies/mL (equivalent to Ct=36.18).

Viral load Negatives

The threshold to declare a viral load negative is the LLOD.

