Table	1.162	Summary of Absolute Viral Load (log 10 copies/mL) as measured by qRT-PCR from Nasal/oropharyngeal swabs for Subjects with missing Baseline Viral Load	Safety	Interim, Final
Table	1.163	Summary of Absolute Viral Load (log 10 copies/mL) as measured by qRT-PCR from Nasal/oropharyngeal swabs for Subjects with Baseline Viral Load	Safety	Interim, Final
Table	1.164	Summary of Change from Baseline in Viral Load (log 10 copies/mL) as measured by qRT-PCR from Nasal/oropharyngeal swabs	Virology	Interim, Final

This document is confidential.

Table	1.171	Summary of Absolute Viral Load (log 10 copies/mL) as measured by qRT-PCR from Nasal/oropharyngeal swabs by Variant of Concern (VOC)/ Variant Under Investigation (VUI)	Safety	Interim, Final
Table	1.172	Summary of Change from Baseline in Viral Load (log 10 copies/mL) as measured by qRT-PCR from Nasal/oropharyngeal swabs by Variant of Concern (VOC)/ Variant Under Investigation (VUI)	Virology	Interim, Final
Table	1.18	Proportion of subjects with undetectable viral load as measured by qRT-PCR from Nasal/oropharyngeal swab through Day 28	Safety	Interim, Final
Table	1.19	Summary of Proportion of Epitope substitutions at Baseline, Post-Baseline by VOC/VUI - Consensus Sequence (Allelic frequency >50%)	Safety	Interim
Table	1.20	Summary of Proportion of Treatment Emergent Epitope substitutions by VOC/VUI - Consensus Sequence (Allelic frequency >50%)	Safety	Interim
Table	1.21	Summary of Proportion of Epitope substitutions at Baseline, Post-Baseline by VOC/VUI - Minority species (Allelic frequency >5%)	Safety	Interim
Table	1.22	Summary of Proportion of Treatment Emergent Epitope substitutions by VOC/VUI - Minority species (Allelic frequency >5%)	Safety	Interim
Table	1.231	Summary of Absolute in Viral Load (log 10 copies/mL) as measured by qRT-PCR from Nasal/oropharyngeal swabs for Epitope Substitutions by Residue	Safety	Interim, Final
Table	1.232	Summary of Change from Baseline in Viral Load (log 10 copies/mL) by Baseline, Post-Baseline Epitope substitution (>=3 subjects)	Virology	Interim, Final
Table	1.241	Summary of Absolute in Viral Load (log 10 copies/mL) by Treatment-Emergent Epitope substitution (>=3 subjects)	Safety	

This document is confidential.

				Interim, Final
Table	1.242	Summary of Change from Baseline in Viral Load (log 10 copies/mL) by Treatment-Emergent Epitope substitution (>=3 subjects)	Virology	Interim, Final
Table	1.25	Summary of Clinical Outcomes	Completer (IA) Safety (FA)	Interim, Final

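### The undetectable-virus proportion (SAP 10.2, Table 1.18) is planned on the Safety Set only, so it cannot be read as clearance after sotrovimab; a Virology Set version and Day 0 counts should be added

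*SAP*

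**What the plan says.** SAP Section 10.2 counts a patient as having undetectable virus when viral load is below the LLOD (453 copies/mL, SAP 8.2). It tabulates this at Day 7, 14 and 28, and fixes the population: "Summary of proportion of patients with undetectable virus would be based on safety population". The SAP Index of Tables (Section 14) lists Table 1.18, "Proportion of subjects with undetectable viral load as measured by qRT-PCR from Nasal/oropharyngeal swab through Day 28", under Safety. Exploratory Table 1.50, the same summary in patients with clinical outcomes, is also under Safety.

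SAP 7.2 sets no baseline viral-load condition: "The Safety Set (SS) will include all participants who were enrolled and exposed to study intervention". Protocol 8.2.1 asks at entry for "A positive PCR or antigen test for SARS-CoV-2 through clinical testing or routine screening undertaken as part of clinical management". It does not ask for the central Day 0 swab to be positive, and the protocol itself states no limit on days since the qualifying test.

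The SAP also defines a set that does carry the condition. Under SAP 7.3 the Virology Set requires, at baseline, a "positive PCR test by GOSH qPCR having Viral load above lower limit of detection". SAP 10.2 and the index use it for change from baseline in viral load (Tables 1.164, 1.172, 1.232 and 1.242; Figure 1.1), but not for the undetectable proportion.

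**The concern.** A patient below LLOD on the Day 0 swab has no detectable virus left to lose in this assay. In Table 1.18 that patient still enters every visit's denominator and, if below LLOD at the visit, the numerator. The published proportion is then a blend of two groups.

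Readers will be inclined to take it as clearance. SAP 9.3 and 9.4 label patients above LLOD at Day 28 as not having cleared the virus, and Protocol 8.5 remarks: "While undetectable viral load is a goal for treatment". The study has one treated group, and its interim and final reports go to the MHRA. Without a second table, the reader cannot tell how much of the figure reflects patients in whom no virus was found before treatment took effect.

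**Working it through.** **1. The plan's own figure.** The documents give no expected value for this endpoint. The nearest figure is the precision statement in Protocol 8.5, set for the primary endpoints: N = 500, P = 50%, 95% CI 45.5%–54.5%, by the continuity-corrected score interval. With z = 1.96 and z² = 3.84, both limits use √(z² ∓ 2 − 1/n + 4p(n(1−p) ± 1)) = √503.84 = 22.45, and 1.96 × 22.45 = 43.99.

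- Lower: (500 + 3.84 − 1 − 43.99) / (2 × 503.84) = 0.455
- Upper: (500 + 3.84 + 1 + 43.99) / (2 × 503.84) = 0.545

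The figure reproduces. Half-widths at N = 500 are therefore about 4 points (Table 2 widths: 0.078 at 25%, 0.089 at 50%).

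**2. The effect of the population.** Define, at a given visit:

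- q: share of the Safety Set below LLOD at Day 0
- u: share of those patients below LLOD at the visit
- p: proportion below LLOD among patients detectable at Day 0 (the Virology Set figure)

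If every patient has a Day 0 result, the Safety Set figure is s = (1 − q)p + qu, so the shift is s − p = q(u − p). It is positive whenever Day 0 negatives are undetectable at the visit more often than Day 0 positives.

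**3. Size.** The documents give none of q, u or p, so all values below are assumptions. Shift in percentage points:

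| q | u | p = 20% | p = 50% | p = 80% |
|---|---|---|---|---|
| 5% | 100% | +4.0 | +2.5 | +1.0 |
| 10% | 100% | +8.0 | +5.0 | +2.0 |
| 20% | 100% | +16.0 | +10.0 | +4.0 |
| 5% | 90% | +3.5 | +2.0 | +0.5 |
| 10% | 90% | +7.0 | +4.0 | +1.0 |
| 20% | 90% | +14.0 | +8.0 | +2.0 |

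Example: q = 10%, p = 20%, u = 100% gives 0.10 × (1.00 − 0.20) = 0.08. If q = 0 the shift is zero throughout.

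**4. In counts.** Take 500 patients, q = 10%, p = 50%, u = 100%. The Virology Set gives 225/450 = 50.0% (95% CI 45.3–54.7). The Safety Set gives (225 + 50)/500 = 55.0% (50.5–59.4). The 5-point gap is slightly more than the half-width of either interval.

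**5. Whether another planned table fills the gap.**

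- Tables 1.162 and 1.163 split by missing or available baseline viral load, but only for absolute values.
- Table 1.164 uses the Virology Set, but summarises change in log10 copies/mL, not the proportion undetectable.
- Table 1.42 describes patients still above LLOD at Day 28, on the Safety Set.
- SAP 8.6 plans no subgroups.

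None gives the proportion undetectable among patients detectable at Day 0. The table shells are a separate document, so a Day 0 row in Table 1.18 cannot be ruled out, but the SAP text does not require one.

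**The case against.** The strongest reply is that the SAP does what the protocol asks. Secondary Objective 2 is the proportion of patients undetectable at each visit: a point prevalence among treated patients, with no baseline-positive condition. The Safety Set delivers that. This stands, and it rules out calling the table an error or a departure from the protocol. It also weighs against making the Virology Set the lead population, which would narrow the protocol's denominator after the interim analysis has been run.

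Several stronger readings that a reader might infer also fail:

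- *Every Day 0 negative counts as undetectable later.* Such a patient counts only if below LLOD at that visit, and the rebound rule in SAP 10.2 provides for virus becoming quantifiable after being below LLOD.
- *These patients had cleared the virus before treatment.* Protocol 8.9 acknowledges false negatives and virus elsewhere in the respiratory tract. Eligibility also depends on a commissioning policy that is not in the documents, so how late patients can present is unknown.
- *This is the only clearance-related measure.* Tables 1.42, 1.44 and 1.164 also bear on it.
- *The inflation is known and large.* It rests wholly on assumed inputs, and it shrinks as p rises, so it would be smaller at later visits if more patients have become undetectable by then.

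The reply can add that the Virology Set drops patients with no baseline result, whose follow-up swabs are valid for the protocol's endpoint. It can also say that set sizes in column headings (SAP 12.2.4) and patient listings disclose much of this. The first is a reason to keep both versions. The second helps only in part: a difference in set sizes does not separate Day 0 negatives from missing Day 0 results, and listings do not supply the missing proportion. Finally, the study is descriptive and no decision rule uses this figure, which limits the stakes.

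**Conclusion.** The point holds as one of interpretation. Table 1.18 on the Safety Set is a legitimate answer to the protocol's endpoint, but it is not a measure of clearance after sotrovimab, and the SAP requires no table that is the proportion-based counterpart in patients detectable at Day 0.

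The direction is upward under the mild assumption u > p. The size is unknown. Over assumed q of 5–20% and u = 100% it runs from +1 point (q = 5%, p = 80%) to +16 points (q = 20%, p = 20%), and it is zero if nobody is below LLOD at Day 0. At the upper end it exceeds the sampling error at N = 500; at the lower end it does not. These figures assume that every patient has a Day 0 result. This is a cheap improvement that should be made before the final analysis, not a flaw that invalidates the endpoint.

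**What to change.** In SAP 10.2 and the Index of Tables:

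1. Keep Table 1.18 on the Safety Set as the protocol-specified analysis.
2. Add the same table on the Virology Set, and say that any statement about clearance will rest on that version.
3. In the Safety Set table, show at Day 0 the number and proportion below LLOD and, separately, the number with no result. SAP 8.3 lists Ct > 45 under missing in its post-baseline imputation table, so state on which side of that split a Day 0 swab with Ct > 45 falls.

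Changing the population of exploratory Table 1.50 is optional.

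The cost is a few lines of SAP text and one extra table from an existing set and existing data. The added table will have a smaller denominator, because patients with no baseline result also drop out, and will probably show a less favourable figure.

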6.2. Rationale

Since December 2020, a number of variants of SARS-CoV-2 have emerged globally, with a high level of uncertainty around their transmissibility, severity and potential for evading vaccine-induced immunity or developing resistance against antivirals and mAbs. SARS-CoV-2 variants can undergo mutations that alter the AAs in the spike protein of the virus [Harvey W.T, 2021]. In the UK, many of these variants have been detected and have since remained under surveillance by UKHSA through routine surveillance [UKHSA, 2021]. Variants may be designated as VOC or VUI, depending on the evidence at the time of their discovery.

Sotrovimab is an early treatment that will be prescribed to SARS-CoV-2 patients at risk to progress to severe disease in non-hospitalised settings. There is a theoretical risk of monoclonal antibodies selecting for viral variants which could have the potential for increased transmissibility and/or reduced susceptibility to sotrovimab or to vaccine-derived immunity. IC patients, who are on a prioritised list to receive treatment should they become infected, present a particular risk for variants because of their potential for prolonged viral shedding, and thus, present a risk for the emergence of mutations and potential onward community transmission.

Thus, this genomic surveillance study will aim to describe changes in the SARS-CoV-2 spike protein observed in IC patients receiving sotrovimab in sentinel sites at a national level to assess potential emergence of viral variants.

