8.3 Missing Data

For participants who are withdrawn from the study prior to the end of the study, all data collected up to the point of discontinuation will be used for analysis.

Imputation will be performed on post-baseline viral loads depending on the viral load results as below:

This document is confidential.

Viral loads that are missing or less than the LLOD (453) will be imputed as $0.5 \times \text{LLOD} = 0.5 \times 453 = 226.5$ copies/ml = 2.36 log10c/ml.

Viral loads that are above the LLOD but lower than the LLOQ (1570) will be imputed as $\text{LLOQ} - 0.5 \times (\text{LLOQ} - \text{LLOD}) = 1570 - 0.5 \times (1570 - 453) = 1011.5$ copies/ml = 3.00 log10c/ml.

Possible VL results	LLOD	LLOQ	Reported in the listings as:	Imputation for analysis:
Missing (as Ct>45)	453	1570	NEG	Half LLOD = 226.5 copies/ml = 2.36 log10c/ml
<LLOD, e.g. 400	453	1570	NEG	Half LLOD = 226.5 copies/ml = 2.36 log10c/ml
Between LLOD and LLOQ, e.g. 1000	453	1570	<1570	LLOQ - 0.5*(LLOQ-LLOD) = 1011.5 copies/ml = 3.00 log10c/ml
>LLOQ, e.g 2000	453	1570	Numeric result	None – use numeric result

For calculating age, birth date will be imputed as follows:

For all subjects, the missing date and month will have this imputed as '30th June'.

Birth date will be presented in listings as 'YYYY'.

Completely missing dates of birth will remain as missing, with no imputation applied. Consequently, the age of the subject will not be calculated and will remain missing.

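### Change from baseline in viral load by variant and epitope group mixes baseline level with decline once values fall below the LLOD, and no planned table shows how many do in each group

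*SAP*

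**What the plan says.** SAP 10.2, under viral load, plans that actual and "change from baseline values will also be summarized by VOC/VUI variants, and for Epitope Substitutions by Residue". The outputs in SAP section 14 are Table 1.172 (change by VOC/VUI), Table 1.232 (change by baseline and post-baseline epitope substitution) and Table 1.242 (change by treatment-emergent epitope substitution). The two epitope tables admit groups of three or more subjects. Overall change is in Table 1.164 and Figure 1.1.

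Three definitions determine what these outputs can show:

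- SAP 8.2 defines change as the post-baseline value minus the baseline value, and puts the LLOD at 453 copies/mL and the LLOQ at 1570.
- SAP 8.3 applies to post-baseline results: "Viral loads that are missing or less than the LLOD (453) will be imputed as" half the LLOD, 226.5 copies/mL or 2.36 log10. Results between LLOD and LLOQ become 1011.5 copies/mL, or 3.00 log10.
- Change is summarised in the Virology Set, which SAP 7.3 limits to patients with a positive baseline PCR "having Viral load above lower limit of detection" (at or above it, as the section goes on to say).

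The SAP names no censored-data method and no baseline adjustment for these summaries. The proportion undetectable is tabulated overall (Table 1.18) and in subjects with clinical outcomes (Table 1.50). No indexed table gives it by variant or epitope group.

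**The concern.** A patient below the LLOD at follow-up contributes a change that depends only on where that patient started. If variant or epitope groups differ in Day 0 viral load, their mean and median changes will differ even when the virus declines equally in all of them. In the other direction, a real difference in decline shrinks as more patients reach the floor.

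This matters because Protocol 6.2 names reduced susceptibility to sotrovimab as a concern. Someone looking for a sign of it would turn naturally to viral decline by variant or by epitope substitution. As planned, that reader could not tell how much of a cell is measured decline and how much is the constant.

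**Working it through.** **Inputs from the SAP.** LLOD 453, LLOQ 1570, the imputation rule (8.3), the definition of change (8.2), and baseline at or above the LLOD (7.3).

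**Inputs assumed.** Baseline means, baseline SD, and mean and SD of decline. The documents give none of these.

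**1. The plan's own figures reproduce.**
- 0.5 × 453 = 226.5, and log10(226.5) = 2.355, given as 2.36.
- 1570 − 0.5 × (1570 − 453) = 1011.5, and log10(1011.5) = 3.005, given as 3.00.
- log10(453) = 2.656.

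**2. Change for a floored patient.** Change = 2.355 − baseline, which is also the largest fall the method can record:

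| Baseline (log10) | Recorded change |
|---|---|
| 2.656 (the LLOD) | −0.30 |
| 4 | −1.65 |
| 5 | −2.65 |
| 6 | −3.65 |
| 7 | −4.64 |

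For a group with share f below the LLOD, mean change = f × (2.355 − mean baseline of the floored patients) + (1 − f) × (mean change of the others). The first term carries only baseline, and its weight is f.

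**3. What the documents say about f.** Protocol 8.5 states: "It is also anticipated that in some patients, the viral load in samples collected at days 7, 14, and 28" will be too low, but this concerns determination of the sequence endpoint, not the 453 copies/mL limit. Its one numerical illustration, for Day 7, is "if there were 400 patients with a detectable viral load and 50% had AA changes that meet the criteria of interest". Set against the target of 500, 1 − 400/500 = 20% not detectable. That reading is an inference, and nothing is given for Day 14 or 28.

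**4. Same true decline, different baseline.** Simulation with the SAP 8.3 rule, baseline SD 1.3 and baselines below the LLOD removed:

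| True mean decline (SD) | Below LLOD at baseline mean 5 / 6 / 7 | Recorded mean change at 5 / 6 / 7 | Spurious gap, 5 v 7 |
|---|---|---|---|
| 1.5 (1.5) | 31% / 17% / 8% (about 19% pooled) | −1.21 / −1.37 / −1.45 | 0.24 |
| 4.0 (1.2) | 82% / 64% / 42% | −2.52 / −3.12 / −3.57 | 1.05 |
| 6.0 (1.5) | 97% / 91% / 80% | −2.71 / −3.55 / −4.36 | 1.65 |

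Medians behave the same way: −2.51 to −3.59 in the second row and −2.68 to −4.38 in the third.

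**5. A closer pair of groups, and the reverse case.** Baseline SD 1.2, SD of decline 1.5. Middle column: baseline means 6.5 and 5.5 (about 0.97 apart after truncation) with identical true decline. Last column: equal baselines of 6 and a true difference in decline of 1.0.

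| Pooled share below LLOD | Spurious difference (truth 0) | Recorded difference (truth −1.0) |
|---|---|---|
| 17-18% | −0.12 | −0.87 |
| 25% | −0.18 | −0.81 |
| 53% | −0.45 | −0.53 |
| 80% | −0.73 | −0.24 |
| 97% | −0.93 | −0.04 |

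At around 20% below the LLOD, roughly 15% of the baseline gap leaks into the change and about 85% of a real difference survives. Baseline dominates only when well over half of the values are floored.

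**The case against.** The strongest reply is that the documents do not establish heavy flooring. A reader might infer that the plan expects most follow-up values below the assay range, so that these tables show baseline rather than decline. The text does not support that. Protocol 8.5 speaks of some patients, in the context of sequencing; its only illustration implies about 20% at Day 7; and Protocol 6.2 says these patients "present a particular risk for variants because of their potential for prolonged viral shedding". It is true that Protocol 8.5 also says "While undetectable viral load is a goal for treatment, this would further reduce the number of patients contributing", but it attaches no rate. This part of the reply stands: the large gaps in the working depend on assumed declines of 4 to 6 log10.

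Other points stand in part:

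- The study is descriptive (Protocol 8.7.1) and no between-group test of viral load is planned. Change in viral load is not a listed endpoint. This limits the consequence, but the descriptive figure itself is still distorted.
- Absolute loads are tabulated for the same kinds of group (Tables 1.171, 1.231, 1.241), and the group plots (Figures 1.2 and 1.3) show absolute medians. A baseline gap would often be visible. However, those tables use the Safety Set while the change tables use the Virology Set, and none shows the share at the floor.
- Treatment-emergent groups (Table 1.242) need a sequenced follow-up sample and so lean towards higher load at that visit. The floor bites less there, although other visits remain exposed.
- The table shells are a separate document that was not available. They may already carry counts below the LLOD; this could not be checked.
- A covariate-adjusted censored model is fragile in groups as small as three, and under very heavy censoring it leans on the assumed normal tail. That argues against making it the main remedy.

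**Conclusion.** The point holds as a limited one. The mechanism follows from SAP 8.2 and 8.3 alone: below the LLOD, change from baseline is a restatement of baseline, and the by-group tables offer no means of seeing how often that happens. The size depends on a share that the documents do not state. For baseline means two log10 apart it runs from about 0.2 log10 at roughly 20% below the LLOD to about 1.65 log10 at 80-97%, under assumed SDs and normal distributions.

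It cannot be said that the planned tables will mainly show baseline; that would need well over half of a group to be floored. The primary endpoints and the overall proportion undetectable (Table 1.18) are not touched. Label: cheap improvement.

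**What to change.** In SAP 10.2, and in the shells for Tables 1.164, 1.172, 1.232 and 1.242 and Figure 1.1:

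1. Print the number and percentage of patients below the LLOD, by group and visit, beside every change-from-baseline summary.
2. Print the group's Day 0 viral load in the Virology Set next to it.
3. Where 50% or more of a group is below the LLOD at a visit, report that percentage in place of mean or median change.
4. Optionally, for the larger VOC/VUI groups only, add a sensitivity analysis: a censored-normal (Tobit) model with Day 0 log10 viral load as covariate and post-baseline values censored at 453 copies/mL.

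The cost is a few lines of SAP text and some added table columns, from data already held. The optional model uses a standard SAS procedure and assumes log-normality. The downside is that some late-visit cells will show a percentage where a mean was expected.
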